6.1 Input Data

Electronic Case Report Forms (eCRF) will be developed by Statistics & Data Corporation (SDC). Data from source documents will be entered into the eCRF by site personnel. All users will complete role-based system and study-specific eCRF training prior to receiving access to the study database. User access will be granted based on a user's role in the study and will be controlled through individual login credentials including a unique User ID and password.

The clinical study database will be developed and tested in iMedNet™ v1.204.0 or higher. iMedNet™ is delivered as a single-instance multi-tenant Software-as-a-Service (SaaS) electronic data capture (EDC) system and is developed, maintained, and hosted by MedNet Solutions located in Minnetonka, Minnesota. Over the duration of the study, MedNet Solutions may apply system updates to the EDC system as part of their continuous improvement efforts.

After data are entered into the clinical study database at each milestone, described in [Section 2.7](#), electronic edit checks and data review will be performed. All data validation specifications and procedures are detailed in the Data Validation Manual as a separate document. When the database has been declared to be complete and accurate, the database will be locked. Any changes to the database after data have been locked can only be made with the approval of Tarsus Pharmaceuticals, Inc. in consultation with SDC and per SDC standard operating procedures (SOPs).

Analyses outlined in this document will be carried out after the following have occurred for the first milestone:

- All data management requirements are met according to SDC SOPs, including data entry, performance of edit and validation checks, documentation and resolution of data queries, generation of coding reports, SAE reconciliation, and database lock with written authorization provided by appropriate SDC and Tarsus Pharmaceuticals personnel.
- Protocol deviations have been identified and status determined as major or minor as well as the potential impact on the primary efficacy endpoint.
- Analysis populations have been determined.
- Randomized treatment codes have been unmasked

At the second milestone the following will occur:

- All data management requirements are met according to SDCSOPs, including data entry, performance of edit and validation checks, documentation and resolution of data queries,

generation of coding reports, SAE reconciliation, and database lock with written authorization provided by appropriate SDC and Tarsus Pharmaceuticals personnel.

- Protocol deviations have been identified and status determined as major or minor.

6.2 Output Data

Data from electronic data capture (EDC) and external data will be transferred to Biostatistics and incorporated into standard formats following the Study Data Tabulation Model (SDTM). Data will then be mapped to analysis datasets using the Analysis Data Model (ADaM). Both SDTM- and ADaM-formatted data will be used to create the subject listings, while all tables and figures will be based on the ADaM-formatted data.

SDTM will follow the SDTM version 1.7 model and will be implemented using the SDTM Implementation Guide version 3.3 and the latest version of the SDTM Controlled Terminology at the time of study start. ADaM data will follow the ADaM version 2.1 model and will be implemented using the ADaM Implementation Guide version 1.1. Both SDTM and ADaM will be validated using Pinnacle 21 version 3.1.2 or later. Any discrepancies in the validation will be noted in reviewer's guides accompanying the final data transfers.

Define.xml will be created for SDTM and ADaM using the Define-XML version 2.0 model.

7. Analysis Populations

7.1 Full Analysis Set

The Full Analysis Set (FAS) will include all randomized subjects. This population will be the primary population for efficacy analyses and will be used to summarize all efficacy variables. Subjects in the FAS will be analyzed as randomized.

7.2 COVID-19 Analysis Set

The COVID-19 pandemic is continuing during the treatment phase of this study and has impacted the conduct of this clinical study. Challenges from quarantines and potential site closures may lead to difficulties in meeting protocol-specified procedures. Protocol deviations related to COVID-19 will be documented at the subject level. Prior to unmasking, COVID-19-related protocol deviations will be assessed for their significance based on their impact to primary endpoint data.

The COVID-19 analysis set includes all randomized subjects but excludes subjects that discontinued due to COVID-19 complications, subjects that would have discontinued due to COVID-19 had they remained on study, and subjects that had significant COVID-19-related protocol deviations. Subjects that would have discontinued due to COVID-19 had they remained on study will be determined and documented prior to unmasking. Protocol deviations will be assessed prior to unmasking for their significance based on their impact to primary endpoint data. Sensitivity analyses of the primary efficacy and key secondary analyses will be performed on the COVID-19 population and subjects will be analyzed as randomized if at least 5% of subjects met these criteria.

7.3 Per-Protocol Set

The per-protocol (PP) set will include subjects in the FAS who do not have significant protocol deviations that potentially could effect the primary endpoint analyses. Protocol deviations will be assessed prior to unmasking. Subjects in the PP set will be analyzed as treated.

This population will be the secondary population for efficacy analyses and will be used to summarize a subset of efficacy variables. If the PP and FAS populations are exactly the same, then additional efficacy analyses on the PP population will not be performed.

7.4 Safety Set

The Safety set will include all randomized subjects who have received at least one dose of study medication. This population will be used to summarize safety variables and will summarize subjects as treated.

8. General Statistical Considerations

8.1 Unit of Analysis

Safety endpoints will be analyzed for both eyes. For subject-level efficacy endpoints, the unit of analysis will be the subject. For efficacy endpoints assessed on each eye individually, the unit of analysis will be the analysis eye. The analysis eye is defined as the eye that met all of the inclusion criteria. If both eyes met all of the inclusion criteria, then the analysis eye will be the eye with the highest *Demodex* density at the Screening visit or, if both eyes have equal *Demodex* density, the right eye.

8.2 Missing or Inconclusive Data Handling

Missing data due to intercurrent events will be handled as per [Section 2.6](#). For the primary analysis, missing data due to lack of efficacy or AEs will be imputed as failures, and missing data without withdrawal or withdrawal due to reasons other than lack of efficacy or AEs will be imputed employing MI using randomized treatment-based MCMC methodology and is further explained in [Section 13](#).

Partial/missing start and end dates for AEs and concomitant medications will be imputed as follows:

Partial/missing start date:

- Dates with missing day only will be imputed as the 1st of the month unless the month and year are same as the month and year of first dose of study medication, in which case missing day will be imputed as the first dose day of study medication.
- Dates with both day and month missing will be imputed as 1 Jan unless the year is same as the year of first dose of study medication, in which case missing day and month will be imputed as the first dose day and month of study medication.
- Completely missing dates will be imputed as the first dose date of study medication unless the end date is on or before the first dose date of study medication, in which case missing date will be imputed as 1 Jan of the same year as the end date.

Partial/missing end date:

- Dates with missing day only will be imputed as the last day of the month unless the month and year are the same as the month and year of the last dose of study medication, in which case missing day will be imputed as the last dose day of study medication.
- Dates with both day and month missing will be imputed as 31 Dec unless the year is same as the year of the last dose of study medication, in which case missing day and month will be imputed as the last dose day and month of study medication.
- If the ongoing flag is missing or “Yes” then the date will not be imputed unless death date is available, in which case the missing date will be imputed as the death date. If ongoing is “No” then the missing end date will be imputed as the last dose date.
- If the imputed date is after the date of death, then the end date will be set equal to the date of death.

The original dates will be displayed in data listings and the imputed dates will be used in derivations only (study day, treatment-emergence status, etc.).

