## 6.5 CONCOMITANT THERAPY

For this protocol, a prescription medication is defined as a medication that can be prescribed only by a properly authorized/licensed clinician. Medications to be recorded in the source document are concomitant prescription medications, over-the-counter medications, supplements, and relevant treatments and/or procedures (e.g., lid scrubs, tea tree oil, etc.). All concomitant medications including over-the-counter medications and nutritional supplements used within the 30 days prior to the first visit will be documented. Any changes to concomitant medication use or initiation of new medications will be reported throughout the study.

For the duration of the study, any therapy considered necessary for the participant's welfare may be given to the participant at the discretion of the investigator. Initiation of new medications or changes to concomitant medications should be recorded in the source document.

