10.1 Demographic Variables

The demographic variables collected in this study include age, sex, childbearing potential, race, ethnicity, and iris color (right eye [OD] and left eye [OS]). Subjects can select more than one race, and they will be categorized as Multiple Race on summaries. Demographic variables will be summarized for the FAS, COVID-19 Analysis Set, PP set, and Safety set separately. Demographic variables will also be summarized by site for the FAS.

Age (years) will be summarized by treatment arm and overall using continuous descriptive statistics as well as dichotomized into age categories of <65 years and ≥65 years. Age will be reported in years and calculated using the age at last birthday.

The number and percentage of subjects will be presented by treatment arm and overall for sex, childbearing potential, race, ethnicity, and iris color (OD and OS).

A subject listing that includes age, sex, race, ethnicity, and iris color will be provided. Childbearing potential will be listed with urine pregnancy results (see [Section 15.2](#)).

Tables and listings for demographics and pre-treatment variables will be generated after the completion of Milestone 1, as described in [Section 2.7](#).

11. Medical History and Concomitant Medications

Tables and listings for medical history will be generated after the completion of Milestone 1, as described in [Section 2.7](#).

As described in [Section 2.7](#), tables, and listings for concomitant medications and procedures with a start date during the on-treatment interval will be generated after Milestone 1. These tables and listings will use all available data and thus, concomitant medications and procedures with start dates during the on-treatment interval and end dates after Day 43/57 will be shown in Milestone 1 tables and listings. After the completion of Milestone 2, the concomitant medication and procedures listings, and the on-treatment interval tables will be re-run to include the Day 90/post-treatment interval data. Additionally, separate tables

for concomitant medications and procedures with start dates during the post-treatment interval will be generated for Milestone 2.

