11.2 Concomitant Medications

Concomitant medications will be coded using World Health Organization Drug Dictionary (WHODrug) Global (B3, March 2020) and summarized by therapeutic drug class (Anatomical Therapeutic Chemical [ATC] 4 classification) and preferred name. If the ATC 4 classification is not provided, the next lowest classification that is provided in the coding dictionary will be used. The preferred name will be defined as the active ingredient; if the active ingredient is not provided or includes more than two ingredients (e.g., multivitamins) then the drug name will be summarized as the preferred name.

Concomitant medications are defined as those medications reported as having been taken (1) prior to initiation of study drug administration and continuing for any period of time following the first administration of study drug or (2) at any time following the first administration of study drug.

Concomitant medications will be summarized using the Safety set. Medications will be tabulated for each treatment arm using frequencies and percentages. Subjects may have more than one medication per ATC text. At each level of subject summarization, a subject will be counted once if he/she reports one or more medications. Percentages will be based on the number of subjects in each treatment arm. The ATC classes and preferred names within an ATC class will be sorted in decreasing frequency among all subjects. Listings of concomitant medications will be generated separately for ocular and non-ocular data (as specified by the investigator), including indication, route of administration, start date, and end date or ongoing.

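### SAP 8.2: two of the three start-date rules ignore the stop date, so a medication that ended before first dose can be given an imputed start on Day 1, after its own stop

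*SAP*

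**What the plan says.** The rules in SAP 8.2 open with "Partial/missing start and end dates for AEs and concomitant medications will be imputed as follows". For start dates there are three:

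- **Day missing.** Use the 1st of the month, unless month and year match those of first dose, "in which case missing day will be imputed as the first dose day of study medication".
- **Day and month missing.** Use 1 January, unless the year matches that of first dose, "in which case missing day and month will be imputed as the first dose day and month of study medication".
- **Completely missing.** Use the first-dose date, "unless the end date is on or before the first dose date of study medication"; in that case use 1 January of the end-date year.

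The only cap on an imputed date applies to end dates, at death. Nothing caps an imputed start at the recorded stop. Listings keep the original dates; otherwise "the imputed dates will be used in derivations only (study day, treatment-emergence status, etc".

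Three other places matter. Protocol 6.5 requires that medications "used within the 30 days prior to the first visit will be documented", so records that stopped before first dose can be expected. SAP 11 says that tables and listings for "concomitant medications and procedures with a start date during the on-treatment interval will be generated after Milestone 1", and SAP 2.7 lets that interval run from screening to Day 43/57. SAP 11.2 defines a concomitant medication as one begun before study drug and continued past first administration, or one taken "at any time following the first administration of study drug".

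**The concern.** Setting an unknown start to the first-dose day is a normal cautious default when the timing cannot be settled. A recorded stop before first dose does settle it: the start must be earlier still. The third rule recognises this and the first two do not. A record with more information (year known) can thus receive an impossible date, while one with less (nothing known) receives a date consistent with its stop.

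At stake are the derived start study day and, depending on programming, whether a medication finished before the study appears as begun on study drug.

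**Working it through.** The plan states no figure here to reproduce, so the check applies the three rules literally to example records.

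**Inputs.** The rules are those of SAP 8.2. The dates are assumptions: first dose on 20 October 2021, which is plausible because SAP 3.1 splits the cohorts by consent at 21/22 October 2021. If Screening and Day 1 fall on the same day, as SAP 3.1 allows, stops on 1 and 5 October are 19 and 15 days before the first visit. Both lie inside the 30-day look-back.

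**Study day** (usual convention without a Day 0, assumed): date minus first dose, plus 1 if on or after first dose. So 1 October gives 1 - 20 = Day -19, 5 October gives 5 - 20 = Day -15, and 20 October gives 0 + 1 = Day 1.

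| Start as recorded | Recorded stop | Imputed start, SAP 8.2 | Start day | Stop day | Start after stop? |
|---|---|---|---|---|---|
| 2021 only | 1 Oct 2021 | 20 Oct 2021 | 1 | -19 | Yes |
| Oct 2021 | 5 Oct 2021 | 20 Oct 2021 | 1 | -15 | Yes |
| Sep 2021 | 1 Oct 2021 | 1 Sep 2021 | -49 | -19 | No |
| 2020 only | 1 Oct 2021 | 1 Jan 2020 | -658 | -19 | No |
| Completely missing | 1 Oct 2021 | 1 Jan 2021 | -292 | -19 | No |

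Only the first two rows fail. They are the cases in which the known part of the start matches first dose and no stop-date check exists.

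**With the third rule's exception added to the other two.** Row 1 becomes 1 January 2021 (Day -292) and row 2 becomes 1 October 2021 (Day -19). Both precede their stops and first dose. The other three rows do not change.

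**Reach.** The day-missing rule fails only if the medication both started and stopped in the first-dose month before first dose, here 1 to 19 October. The year-only rule covers any start from 1 January to 19 October, 292 days in this example. A first dose early in a calendar year leaves little room for the fault; one late in the year leaves a lot.

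**Does the wrong start reach a table?** There are two readings:

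- If status is derived from the imputed start, Day 1 falls inside the on-treatment interval and the record is counted as on-study use.
- If the recorded stop is checked against SAP 11.2, the record meets neither part of the definition and is excluded.

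The SAP does not say which check is programmed. The start study day is wrong under both.

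**The case against.** The strongest reply is that SAP 11.2 already protects the tables. A product that stopped before first dose neither continued past first administration nor was taken after it, whatever start is imputed. The start-date wording in SAP 11 can also be read as dividing output between Milestones 1 and 2, not as defining what is concomitant. Taken as the sole selector, it would drop medications begun before screening and continued, against the first part of the SAP 11.2 definition. This stands: miscounting in the tables is a possibility that depends on programming, not a consequence of the text. It does not rescue the imputed date, which is impossible under any reading.

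A reader might go further and infer that the tables overstate on-study use of the products restricted by Protocol 5.2, and so blur the interpretation of cure. The documents do not support that:

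- The stop-date check may be the one programmed.
- Protocol 6.5 gives lid scrubs and tea tree oil as examples of treatments or procedures. SAP 11.3 handles procedures separately, and the SAP 8.2 date rules name only adverse events and medications. Whether such products would be entered as medications is not stated.
- Significant deviations are judged by masked review, and no efficacy analysis in the documents is shown to use these imputed dates.

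A reader might also infer that pre-treatment adverse events would be counted as treatment-emergent. The logic allows it, but Protocol 8.3.4 records events starting after first dose and treats conditions present at screening as baseline. SAP 14.2 does not expect events before treatment. Such records should scarcely exist.

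**Conclusion.** The drafting error is real and narrow. It affects only starts with a missing day in the first-dose month, or with missing day and month in the first-dose year, whose recorded stop is before first dose. Each such record receives a wrong start study day; counting it as on-study use is conditional on programming. The documents give no count of such records, and it is probably small. The adverse-event route is mainly theoretical, the listings still show the true entries, and the primary test is untouched.

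The third rule's result of 1 January is consistent with the stop date; it is not known to be the true start. The conclusion rests on a literal reading of SAP 8.2 and does not depend on the example dates. This is a minor point, worth correcting because the remedy already stands in the SAP.

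**What to change.** In SAP 8.2, add the third rule's exception to the first two. If the end date is on or before the first-dose date, impute the 1st of the known month (day missing) or 1 January of the known year (day and month missing). Otherwise keep the first-dose day. Add a general line that no imputed start may fall after a recorded stop.

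A stop on the first-dose day itself gives no impossible date either way, so that boundary is a matter of choice, but it should be the same in all three rules. It would also help to state in SAP 11 whether concomitant status is decided by the imputed start, the recorded stop or both.

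The cost is one clause in each of two SAP rules and one condition in the date-imputation program, with no protocol amendment, new data or additional patients.

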8.3 Definition of Baseline

Baseline measures are defined as the last measure prior to the initiation of study treatment. Change from Baseline will be calculated as Follow-up Visit measure – Baseline Visit measure.

8.4 Data Analysis Conventions

All data analyses will be performed by SDC after the study is completed and the database has been locked and released for unmasking. Statistical programming and analyses will be performed using SAS® version 9.4 or higher. Output will be provided in rich text format (RTF) for tables and portable document format (PDF) for tables, listings, and figures using landscape orientation.

Summaries for continuous and ordinal variables will include the number of observations (n), arithmetic mean, standard deviation (SD), median, minimum, and maximum. Minima and maxima will be reported with the same precision as the raw values; means and medians will be presented to one additional decimal place than reported in the raw values. SDs will be presented to two additional decimal places than reported in the raw values. Summaries for discrete variables will include counts and percentages. All percentages will be rounded to one decimal place (i.e., XX.X%). Differences between the active treatment arm and placebo will be calculated as active minus placebo.

All statistical tests will be one-sided with a significance level of 0.025 ($\alpha = 0.025$) unless otherwise specified. Confidence intervals (CI) for differences between treatment arms as well as change from baseline will be two-sided at a 95% confidence level. All p-values will be rounded to 4 decimal places; p-values less than 0.0001 will be presented as “<0.0001”; p-values greater than 0.9999 will be presented as “>0.9999.”

Unless otherwise specified, summaries will be presented by treatment arm and, where appropriate, visit. Listings will be based on all randomized subjects unless otherwise specified, and sorted by subject number, visit/time point, and parameter as applicable.

8.5 Adjustments for Multiplicity

A closed hierarchical testing structure will be used where the analysis will be performed for the primary efficacy endpoint and, only if successful, the analysis will be performed for the three secondary efficacy endpoints using the Hochberg testing strategy. Specifically, if the null hypothesis, H_{01} , is rejected at a one-sided α of 0.025, the study will be considered a success for clinical cure and the family of three secondary efficacy endpoints will be tested using the Hochberg testing strategy with a familywise α of 0.025. If the secondary endpoint with the largest p-value is significant at the 0.025 level, then all three secondary endpoints will be declared statistically significant. If the secondary endpoint with the largest p-value is not significant at the 0.025 level, then the secondary endpoint with the second largest p-value will be tested at the 0.0125 level. If this secondary endpoint is significant at the 0.0125 level, then it and the endpoint with the smallest p-value will be declared statistically significant. If not, the endpoint with the smallest p-value will be tested at the 0.0083 level. If the null hypothesis, H_{01} is not rejected at a one-sided α of 0.025 testing will stop and the three secondary efficacy hypotheses will not be tested.

9. Disposition of Subjects and Protocol Deviations

Subject disposition will be presented in terms of the numbers and percentages of subjects who were randomized to masked study medication with subcategories for those who did or did not dose with the masked study medication; those who were included in the FAS, COVID-19, PP, and Safety sets; and those who completed the study and discontinued from the study. Subjects who do not discontinue from the study will be considered study completers. Subject enrollment and disposition will be summarized by treatment arm and completion/discontinuation will be summarized by treatment arm and site. Percentages will be calculated using randomized subjects as the denominator unless otherwise specified.

The reasons for premature study discontinuation will be summarized by treatment arm for all discontinued subjects. Percentages will be calculated using randomized subjects as the denominator. The reasons for study discontinuation that will be summarized include pregnancy, significant study treatment non-compliance per PI determination, exclusion criterion, reasons relating to COVID-19, AE, and other. Withdrawal due to lack of efficacy will be summarized by treatment arm. A subject listing will be provided that includes the date of and reason for premature study discontinuation.

The number and percentage of subjects with any deviation, major deviation, minor deviation, and the total number of deviations related to COVID-19 will be summarized by treatment arm for all randomized subjects. The protocol deviations that will be summarized include the following categories: informed consent, inclusion/exclusion and randomization, test article/study drug instillation and assignment at site, improper protocol procedures at site, site's failure to report SAE/AE, visit out of window (missed, early, or late), subject non-compliance with test article, subject's use of prohibited concomitant medication, subject's failure to follow instructions, other, COVID-19: visit missed, COVID-19: assessment not performed, and COVID-19: other. A subject listing will be provided that includes the date of the deviation, the deviation code, the deviation description, classification of whether the deviation was judged to be COVID-19 related,

and the classifications of whether the deviations were judged to be major or minor and potential impact on the primary efficacy endpoint based on a masked review.

In addition, subject listings will be provided that include informed consent date, inclusion and exclusion criteria violations, and exclusions from any population, subjects affected by COVID-19, and withdrawal due to lack of efficacy. Details of the study randomization, including randomization date, site, randomized treatment, and actual treatment, will also be included within a subject listing.

Tables and listings for subject disposition and protocol deviations will be generated after the conclusion of Milestone 1 and will be re-run after the conclusion of Milestone 2, as described in [Section 2.7](#).

10. Demographic and Pretreatment Variables

